6.3 Other assessments

6.3.1 *Prior and concomitant illnesses*

Relevant additional illnesses present at the time of informed consent are regarded as concomitant illnesses and will be documented on the appropriate pages of the case report form (CRF).

6.3.2 *Prior and concomitant treatments*

Relevant additional treatments administered to the subjects on entry to the trial or at any time during the trial are regarded as concomitant treatments and must be documented on the appropriate pages of the CRF.

For example in case of insufficient improvement of the symptoms, glucocorticoids may be administered to the subject and again searched for other sources of the allergen.

7. STATISTICS

Details of the statistical analysis of the data collected in this trial will be documented in a Statistical Analysis Plan (SAP) that will be generated by IZKS Mainz and finalized before closing the data base and prior to breaking the blind. The SAP is based on the protocol including all amendments. The document may modify the plans outlined in this protocol; however any major modifications of the primary endpoint definition and/or its analysis will also be reflected in a protocol amendment. Any deviation from the original statistical plan must be described and justified in the final report. The statistical analysis will be conducted by means of SAS®.

7.1 Sample size

Power calculations were based on a one sided level of significance of alpha=0.05. Regulatory guidelines suggest the use of a two-sided level of significance. However, it is extremely improbable that in the time frame of the study the prednisolone arm will be significantly worse than the placebo arm. Power calculations were performed by means of a t-test with a correlation to the baseline value of 0.4. With 40 patients evaluable per protocol the study will have a power of 58% to detect non-inferiority of the placebo arm versus the prednisolone arm with a non-inferiority bound of 7%. The power calculations were done by SAS, Version 9.2.

7.2 Analysis populations

All subjects who signed informed consent / were assigned a randomization number are considered as enrolled/randomized subjects, even if they did not receive any trial treatment.

All subjects who received at least one dose of trial treatment and with at least one available post-baseline assessment of the primary analysis variable, will be included in the Intention-to-treat (ITT) population. This population is the primary analysis population. Within ITT population analyses subjects will be assigned to the treatment to which they were randomized.

The per protocol population are all subjects of the ITT population without any major protocol violation. This population is the primary analysis population.

The safety population comprises all subjects who received at least one dose of trial treatment. In analyses of the safety population subjects will be assigned to the treatment which they actually received.

The analysis populations will be defined prior to unblinding of the study.

7.3 Efficacy analyses

Efficacy:

The analyses will be specified more detailed in the statistical analysis plan (SAP). Descriptive statistics of qualitative data will consist of absolute and relative frequencies. For quantitative data the number of observations, mean, standard deviation, minimum and maximum will be presented.

The primary population for the analyses of efficacy is the randomized Population without major protocol violations.

7.3.1 *Definition and analysis of primary endpoint*

The primary analysis variable is the improvement in FVC (difference after 6 months and baseline). The 6 months and baseline FVC values will be given in percent deviation from the norm values tabulated by Quanjer PH., et al. 2013.

A difference between the changes in placebo and active treatment is considered not significant if FVC differences are < 7%. The working hypothesis of the study is that the placebo is not inferior to the prednisolone intervention.

The improvement in FVC will be compared between groups within an analysis of covariance (ANCOVA). Treatment will serve as a fixed factor and the baseline FVC value as a covariate. The primary analysis population will consist of all randomized patients without any major protocol violations. The two-sided 90% confidence interval for the treatment difference will be calculated. Sensitivity analyses will be performed by analyzing the same analysis model for all randomized patients. Additionally, the primary parameter will be analyzed by ANCOVA with additional terms for sex and height. Center effects will be explored by descriptive statistics. Missing values will not be replaced.

If appropriate, a Bayesian analysis with a suited prior distribution will be considered. This will be specified in the statistical analysis plan (SAP).

7.3.2 *Analysis of secondary endpoints*

All analysis of secondary endpoint will be interpreted purely exploratory. Descriptive statistics will be displayed for all

- Response according to the primary analysis variable: Each patient will be classified as a responder or non-responder. A patient is considered as a responder, if the FVC value after 6 months is more than or equal to 93% of the norm values tabulated by Quanjer PH., et al. 2013 and if the patient did not take any glucocorticoid rescue medication. Responders will be analysed by a Chi-Square Test.
- Forced Vital Capacity (FVC): Relative changes from Baseline after 3 months will be compared between groups by an analysis of covariance (ANCOVA) with treatment as a fixed effect and baseline value as a covariate.
- Desaturation with standardized exercise test for children (O₂ saturation), Borg scale: Relative changes from Baseline after 3 months and 6 months will be compared between groups by an analysis of covariance (ANCOVA) with treatment as a fixed effect and baseline value as a covariate.
- Quality-of-life (PedsQL): Descriptive statistics and exploratory p-values
- Health economics (EQ-5D): Health care costs and utility will be determined and combined with quality of life data. Afterwards they will be compared between treatment groups
- Weight for Height, Open usage of rescue glucocorticosteroids (mg/kg/6 months): Descriptive statistics and exploratory p-values only

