STATISTICAL ANALYSIS	
Efficacy: The primary analysis variable is the improvement in FVC (difference after 6 months and baseline). The 6 months and baseline FVC values will be given in percent deviation from the norm values tabulated by Quanjer PH., et al. 2013. A difference between the changes in placebo and active treatment is considered not significant if FVC differences are < 7%. The working hypothesis of the study is that the placebo intervention is not inferior to the prednisolone intervention.
 
Description of the primary efficacy analysis and population: The improvement in FVC will be compared between groups within an analysis of covariance (ANCOVA). Treatment will serve as a fixed factor and the baseline FVC value as a covariate. The primary analysis population will consist of all randomized patients without any major protocol violations. The two-sided 90% confidence interval for the treatment difference will be calculated. Sensitivity analyses will be performed by analysing the same analysis model for all randomized patients. Additionally, the primary parameter will be analysed by ANCOVA with additional terms for sex and height. Centre effects will be explored by descriptive statistics.
 
Safety: Adverse events will be coded by MedDRA and analysed by descriptive methods. Laboratory values will be displayed by sample characteristics over time and compared between groups by exploratory p-values.
 
Secondary endpoint(s): Secondary endpoints will be displayed by descriptive statistics and compared between groups by exploratory p-values.

SAMPLE SIZE	
To be assessed for eligibility: (n=60) To be allocated to trial: (n=45) To be analyzed: (n=40)

TRIAL DURATION	
First patient in to last patient out (months): 24 Duration of the entire trial (months): 27 Recruitment period (months): 18

PARTICIPATING CENTERS	
About 40 trial sites are planned to participate

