3.5 Measures taken to minimize/avoid bias

3.5.1 Randomization

Patients will be allocated to the two treatments, i.e., oral prednisolone and placebo, in a ratio of 1:1 by central randomization within each age group.

The randomization procedure will not consider the sex of the patients, since no sex-specific responses to prednisolone therapy have been reported yet and are not expected. The randomization list will be generated by the IZKS Mainz using a pseudo-random number generator to ensure that the resulting treatment allocation will be both reproducible and non-predictable.

During inpatient treatment each patient to be included will receive the next consecutive random/patient number from a block of randomization numbers. Study medication will be packed and blinded according to the random list. Each patient medication box will be sent together with the sealed unblinding codes (i.e. envelopes) to the sites. The investigator has to take care that each patient will be provided with the study medication box bearing the correct randomization number.

The randomization list is to be kept confidential and is only accessible to authorized personnel until the code is broken. At the end of the trial, any emergency opening of the envelopes will be controlled after collecting the explanations for unblinding and checking the unused treatment units. The code will be broken regularly only at the end of the study after freezing the statistics database (by checking the data, recording any protocol violations etc.) allowing the collected data to be analyzed.

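### The responder endpoint is given an unadjusted chi-square test; a risk difference adjusted for baseline FVC, with an interval, would use data already collected and say more

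*Protocol*

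**What the plan says.** The Synopsis and Section 3.4 list responder status first among the secondary endpoints; the Synopsis calls this group key. Section 7.3.2 adds that a responder must not have taken rescue glucocorticoids, and fixes the analysis: "Responders will be analysed by a Chi-Square Test". It names no covariate, interval or expected rate.

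The same section compares FVC at 3 months, and desaturation and Borg scale at 3 and 6 months, by ANCOVA with the baseline value as covariate. For weight for height and rescue steroid use it plans "Descriptive statistics and exploratory p-values only". The Synopsis says of the group as a whole: "Secondary endpoints will be displayed by descriptive statistics and compared between groups by exploratory p-values". Section 7.3.2 opens by declaring all secondary analyses purely exploratory, and Section 7.3 promises absolute and relative frequencies for qualitative data.

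The trial's hypothesis is that placebo is not inferior. Section 7.3.1 judges it on 6-month FVC by baseline-adjusted ANCOVA with a 7% bound: "The two-sided 90% confidence interval for the treatment difference will be calculated".

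**The concern.** The responder endpoint re-expresses the primary variable as a yes/no outcome, yet it loses both useful features of the primary analysis: adjustment for the starting value and an interval for the treatment difference. Whether a patient reaches 93% of norm plausibly depends on the starting point. Baseline FVC is collected for everyone, and Section 3.5.1 allocates "in a ratio of 1:1 by central randomization within each age group", so baseline FVC is not balanced by design.

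The trial asks how much worse placebo could be. A chi-square p-value does not answer that, and at this sample size a large deficit can come out as non-significant. At stake is how informative one exploratory result is; the trial's main conclusion is not affected.

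**Working it through.** **Inputs from the protocol.** 40 evaluable patients (Sections 3.2 and 7.1) and 1:1 allocation, hence about 20 per arm. On significance level, Section 7.1: "Power calculations were based on a one sided level of significance of alpha=0.05". On correlation, Section 7.1: "Power calculations were performed by means of a t-test with a correlation to the baseline value of 0.4".

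**Assumed, because the protocol gives none.** Responder rates of 50% to 80%; a correlation of 0.6 as an upper scenario; and illustrative responder margins.

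**The plan's own figure.** Section 7.1 states: "With 40 patients evaluable per protocol the study will have a power of 58% to detect non-inferiority of the placebo arm". That concerns the primary FVC test. It cannot be reproduced independently because no SD is given. Solving backwards with a true difference of 0 gives an SD of the analysed variable of about 11.8 points. No power or precision is stated for the responder endpoint, so there is no figure to reproduce for it.

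**1. What a non-significant chi-square can hide.** The Pearson statistic is d² / [p(1−p)·2/20], with p the pooled rate.
- 15/20 v 9/20: d = 0.30, p = 24/40 = 0.60; 0.09 / (0.24 × 0.1) = 3.75; p-value 0.053.
- 16/20 v 11/20: d = 0.25, p = 27/40 = 0.675; 0.0625 / (0.2194 × 0.1) = 2.85; p-value 0.091.

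Interval for the first table: SE = √(0.75×0.25/20 + 0.45×0.55/20) = √0.02175 = 0.1475. The 90% interval for the placebo deficit is 0.30 ± 1.645 × 0.1475, or 6 to 54 points. The 95% Wald interval is 1 to 59 points. It just excludes zero because it uses the unpooled variance, whereas the chi-square pools.

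**2. Power and size of the chi-square** (exact enumeration, 20 per arm, two-sided 0.05).

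| True rates, prednisolone v placebo | Power |
|---|---|
| 70% v 60% | 10% |
| 70% v 50% | 25% |
| 75% v 50% | 38% |
| 75% v 45% | 49% |

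With equal rates it rejects in 4.3% (50%), 5.3% (70%) and 5.1% (75%) of trials, so its size is acceptable.

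**3. What adjustment gains.** Suppose 6-month FVC is normal, has correlation r with baseline, and is cut at the response threshold. The squared correlation of the binary outcome with baseline is then r²·k, where k = φ(z)²/[p(1−p)], φ is the normal density and z the normal quantile at p. Fitting one covariate in 40 patients costs a factor of 1 + 1/36. The net variance ratio is (1 − r²k)(1 + 1/36).

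| Responder rate | k | Reduction, r = 0.4 | Reduction, r = 0.6 |
|---|---|---|---|
| 50% | 0.637 | 8% | 21% |
| 75% | 0.539 | 6% | 17% |
| 80% | 0.490 | 5% | 15% |

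Simulations give much the same: about 4 to 9% at r = 0.4 and about 16 to 19% at r = 0.6, with the adjusted test keeping a type I error of about 5%. For 75% v 45%, power rises from about 50% to 53 to 54% (r = 0.4) or about 59% (r = 0.6).

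**4. What the interval will show.** Before adjustment the 90% half-width is 1.645 × √[2p(1−p)/20]: 26 points at 50%, 23 at 75%, 21 at 80%. Against illustrative margins of 10, 15 and 20 points, non-inferiority power at 20 per arm is 16–20%, 24–32% and 35–48%. Power of 80% would need 396–620, 176–276 and 100–156 patients in total.

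**The case against.** The strongest defence is that the test is being judged against a task the protocol does not set. Section 7.3.2 calls every secondary analysis purely exploratory, and non-inferiority is decided on 6-month FVC alone. A reader might infer that the plan will take a large responder p-value as support for non-inferiority; no section says so. A reader might also extend the criticism to all secondary endpoints. That fails for 3-month FVC, desaturation and Borg scale, whose baseline-adjusted ANCOVA already yields an adjusted difference. It also fails as a general demand for intervals, since the protocol leaves such reporting detail to the SAP, which is not at hand.

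Two further points stand. Frequencies per arm will be reported, so a 75% v 45% result would be visible beside its p-value. The chi-square is also a valid test of a randomised binary comparison, as its size above shows.

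On adjustment, the defence says the yield is negligible at the protocol's own correlation. It is small, and the 0.6 scenario has no source in the document. What the defence does not remove is that the protocol names a specific method for this endpoint, and a better one is available from data already collected and consistent with the neighbouring analyses.

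**Conclusion.** The point holds as a modest improvement to one exploratory analysis. The chi-square is not wrong. It discards baseline FVC and gives no interval for the size of the difference, which is the scale on which this trial asks its question. A 30-point observed placebo deficit at 20 per arm gives p = 0.053, with a 90% interval of 6 to 54 points.

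The main benefit is the interval. The precision gain is about 4 to 9% of variance at r = 0.4. These figures rest on assumed responder rates and a normal model for FVC. The rescue-medication condition in the Section 7.3.2 definition could weaken the link to baseline and shrink the gain.

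It would be too strong to say that the change makes the endpoint informative about non-inferiority: 40 patients are too few at any of the margins tried.

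**What to change.** In Section 7.3.2, replace the chi-square sentence with: the difference in responder proportions (placebo minus prednisolone), adjusted for baseline FVC by standardisation from a logistic or linear model, with its two-sided interval. Use 90% to match the primary analysis, or 95%, and state which. Name the variance method, and a fallback such as the linear model if the logistic fit fails in a small sample. Keep the counts and percentages per arm.

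No change is needed for 3-month FVC, desaturation or Borg scale.

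The cost is one sentence and minor programming, with no extra patients, visits or data. Section 7 lets the SAP modify the protocol's analyses and reserves amendments for major changes to the primary endpoint, so the SAP can carry this before unblinding. The downside is an interval that will look wide, which reflects what 40 patients can show.

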7.3.3 Analysis of Subgroups

If appropriate, subgroups will be defined in the SAP.

7.3.4 Interim analyses

No interim analyses are planned.

7.4 Analysis of adverse events

All summaries and listings of safety data will be performed for the safety population.

Frequencies of subjects experiencing at least one adverse event (AE) will be displayed by body system and preferred term according to MedDRA terminology. Detailed information collected for each AE will include: A description of the event, duration, whether the AE was serious, intensity, relationship to trial drug, action taken, clinical outcome. Summary tables will present the number of subjects observed with AEs and corresponding percentages. Additional subcategories will be based on event intensity and relationship to trial drug.

A subject listing of all AEs will be prepared.

7.5 Analysis of clinical laboratory findings

Listings will be prepared for each laboratory measure and will be structured to permit review of the data per subject as they progress on treatment.

Summary tables will be prepared to examine the changes of laboratory measures over time. Additionally, shift tables will be provided to examine the changes of laboratory data from normal baseline to values outside the corresponding reference range during/after treatment.

8. QUALITY CONTROL AND QUALITY ASSURANCE

8.1 Requirements for investigational sites and staff

The investigator should be able to demonstrate (e.g. based on retrospective data) a potential for recruiting the required number of suitable subjects within the agreed recruitment period.

The investigator should have sufficient time to properly conduct and complete the trial within the agreed trial period.

The investigator should have available an adequate number of qualified staff and adequate facilities for the foreseen duration of the trial to conduct the trial properly and safely.

The investigator should ensure that all persons assisting with the trial are adequately qualified, informed about the protocol, any amendments to the protocol, the trials treatments, and their trial-related duties and functions.

8.2 Direct entries

Data entries be entered in the CRF as Direct, are listed in the Monitor Manual in the section source data control.

8.3 Direct access to source data/documents

The investigator/institution must permit trial-related monitoring and auditing, as well as inspections by the appropriate competent authority and Ethics committees, providing direct access to source data/documents (Confidentiality see 10.3).

The subjects will be informed that representatives of the sponsor, independent ethics committee (IEC) or competent authority may inspect their medical records to verify the information collected, and that all personal information made available for inspection will be handled in strictest confidence and in accordance with local data protection laws.

8.4 Investigator site file and archiving

The investigator will be provided with an investigator site file (ISF) at the start of the trial. The investigator will archive all trial data and relevant correspondence in the ISF. The ISF, all source data and all documents will be kept filed according to the requirements of the ICH-GCP guidelines after termination of the trial.

After the end of the trial trial related documents e.g. trial master file (TMF) and CRFs will be stored in the archive of the sponsor.

It is the responsibility of the investigator to ensure that the subject-identification sheets are stored for at least 15 years beyond the end of the clinical trial. All original subject files must be stored for the longest possible time permitted by the regulations at the hospital, research institute, or practice in question. If archiving can no longer be maintained at the site, the investigator will notify the sponsor.

8.5 Monitoring

Monitoring will be done by personal visits from a clinical monitor according to SOPs of the IZKS Mainz.

Each site will be visited by the monitor at regular intervals to ensure compliance with the trial protocol, GCP and legal aspects. The monitor will review the entries into the eCRF for completeness and correctness and verify the entries on the basis of the source documents.

The presence of correct informed consents will be checked for every subject.

Details will be specified in the monitoring manual for this trial.

The investigator must allow the monitor to look at all relevant documents and must provide support at all times to the monitor.

By frequent communications (letters, telephone, fax), the monitor will ensure that the trial is conducted according to the protocol and regulatory requirements.

8.6 Inspection by authority and audits

Competent authority and by the sponsor authorised persons (auditor) may request access to all source documents, CRF, and other trial documentation in case of an inspection or audit. Direct access to these documents must be guaranteed by the investigator who must provide support at all times for these activities. Source data documents can be copied during inspection or audit in case the identity of the subject have been made unrecognizable.

8.7 Audits

No audits are planned for this trial.

9. DATA MANAGEMENT

The Central Information Office Marburg is responsible for data management. All data management activities will be done according to the current Standard Operating Procedures (SOPs) of Central Information Office Marburg.

For reports and analysis the EDC system provides data export functionality for data management. The data can be exported in SAS or SPSS format for reports and analysis.

9.1 Subject identification database (IDAT)

The IMBEI Mainz is responsible for programming the subject identification database (IDAT) and its hosting. This database contains names and addresses of the subjects and for each subject a unique subject ID. This subject ID is used for all documentation on eCRF and Data Clarification Forms (DCF).

